9.2 Efficacy and PK/PD Variables

The efficacy variables include

- Clinical response
- Cytogenetic response
- The PK and PD variables will include:
 - Determination of the PK of INCB018424 by measuring plasma concentration time profiles.
 - Determination of PD markers including % inhibition of STAT3/5 protein phosphorylation

9.2.1 Efficacy and PK/PD Analysis

Efficacy analyses will be exploratory in nature. All efficacy measures will be estimated with 95% confidence intervals at the dose used in the expanded cohort. The clinical response and the hematological response will be estimated with 95% confidence intervals at each time point. The response rates over time may be analyzed graphically or using a statistical model.

The PK parameters of INB018424 will be summarized using descriptive statistics, and the log-transformed INCB018424 PK parameters will be compared using a 1-factor analysis of variance. The mean values of the PK parameters may be compared to historical data in healthy volunteers to determine if the INCB018424 PK profile is different between patients with hematological malignancies and healthy patients.

For each patient who has taken study medication, the PD parameters will be calculated to explore preliminary evidence of PD activity by assessing the

effect of INCB018424 on pre- and post-dose. If the p-STAT3/5 signaling data are sufficiently robust, an exploratory PK/PD analysis will be performed.

9.3 Safety Analysis

The clinical safety data (vital signs, ECGs, routine laboratory tests and adverse events) will be analyzed using summary statistics (e.g., mean, frequency) and no formal statistical comparisons among the treatment groups are planned.

9.3.1 Adverse Events

Severity of adverse events will be based on the NCI–CTCAE v3.0 (NCI Common Terminology Criteria for Adverse Events, Publ. Aug 9, 2006). The subset of adverse events that are considered by the Investigator to have a possible or probable relationship to study medication will be considered to be treatment-related adverse events. If the Investigator does not specify the relationship of the adverse event to study medication, the adverse event will be considered to be treatment-related. The incidence of adverse events and treatment-related adverse events will be tabulated.

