8. REGULATORY AND REPORTING REQUIREMENTS

Adverse event reporting will be as per the current NCI criteria and the MDACC Adverse Event Reporting Policy for Leukemia Phase I and early Phase II studies.

The descriptions and grading scales found in the revised NCI Common Terminology Criteria for Adverse Events (CTCAE) version 3.0 will be utilized for adverse event reporting. (http://ctep.cancer.gov/reporting/ctc.html).

Serious Adverse Event Reporting (SAE)

A serious adverse event is – any adverse drug experience occurring at any dose that results in any of the following outcomes:

- Death
- A life-threatening adverse drug experience any adverse experience that places the patient, in the view of the initial reporter, at immediate risk of death from the adverse experience as it occurred. It does not include an adverse experience that, had it occurred in a more severe form, might have caused death.
- Inpatient hospitalization or prolongation of existing hospitalization
- A persistent or significant disability/incapacity a substantial disruption of a person's ability to conduct normal life functions.
- A congenital anomaly/birth defect.

Important medical events that may not result in death, be life-threatening, or require hospitalization may be considered a serious adverse drug experience when, based upon appropriate medical judgment, they may jeopardize the patient or subject and may require medical or surgical intervention to prevent one of the outcomes listed in this definition. Examples of such medical events include allergic bronchospasm requiring intensive treatment in an emergency room or at home, blood dyscrasias or convulsions that do not result in inpatient hospitalization, or the development of drug dependency or drug abuse (21 CFR 312.32).

- Important medical events as defined above, may also be considered serious adverse events. Any important medical event can and should be reported as an SAE if deemed appropriate by the Principal Investigator or Sponsor.
- All events occurring during the conduct of a protocol and meeting the definition of a SAE must by reported to the IRB in accordance with the timeframes and procedures outlined in "University of Texas M. D. Anderson Cancer Center Institutional Review Board Policy". SAEs must be reported to the IRB and the Sponsor (Safety Project Manager) regardless of attribution.
- All life-threatening or fatal events with possible, probable or definite attribution

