9.1.1 Selection of Sample Size

This phase II study will use a Gehen's design. Assuming a null response rate of 0%, targeting a 15% response rate and power=80%, the trial will initially enroll 10 patients in each disease category: 1) AML; 2) ALL; 3) MDS; and 4) CML. If at least one response is achieved in the 10 patients in a disease

Category, then a total of 30 patients will be enrolled in this disease category. Thirty patients will provide a confidence interval for response rate with half-width=0.13, assuming the true response rate is 15%. The total sample size is 120.

For toxicity evaluation, patients enrolled in the study will be considered in 2 cohorts (I) those with relapsed/refractory AML, ALL, and MDS (including CMML), and blast phase CML, and (II) those with chronic phase CML. At any time after 6 patients are enrolled in cohort I (including AML, ALL, MDS, blast phase CML patients), if 30% or more patients experience grade 3 or 4 toxicity thought to be directly related to INCB018424 and lasting longer than 2 weeks, then we will stop that cohort of the trial. At any time after 6 patients are enrolled in cohort II (including chronic phase CML patients), if 15% or more patients experience grade 3 or 4 toxicity thought to be directly related to INCB018424 and lasting longer than 2 weeks, then we will stop that cohort of the trial.

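### As written, Section 9.3.1 would leave events rated definite out of the treatment-related adverse event table, while counting events with no attribution

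*Combined protocol and SAP*

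**What the plan says.** Section 9.3.1 (Adverse Events) defines the related subset as the events that the investigator considers to "have a possible or probable relationship to study medication will be considered to be treatment-related adverse events". It then adds a default, which opens "If the Investigator does not specify the relationship of the adverse event to study medication" and assigns such events to the related group. The output follows: "The incidence of adverse events and treatment-related adverse events will be tabulated".

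Section 8 (Regulatory and Reporting Requirements), in the rule for a written report within 24 hours, uses a longer list of levels: "All life-threatening or fatal events with possible, probable or definite attribution" to the study drug. The same section requires serious adverse events to go to the IRB and the sponsor whatever their attribution.

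The stopping rule in Section 9.1.1, repeated in Section 4.1, has separate wording. It counts "grade 3 or 4 toxicity thought to be directly related to INCB018424 and lasting longer than 2 weeks".

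**The concern.** The two sections do not use the same attribution levels, and the level missing from the analysis section is the strongest one. An analyst who programs Section 9.3.1 as it stands obtains a related-event table that includes events of unknown cause and leaves out those most firmly ascribed to the drug.

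Safety and tolerability is the first of the two secondary objectives in Section 1. The trial is open label and non-randomized (Section 4.2), and Section 9.3 plans summary statistics only. Without a control arm, in patients whose disease itself produces many events, investigator attribution is the main planned means of separating drug effects from disease effects. The related-event table is where that attribution is reported.

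**Working it through.** There is no figure in the plan to reproduce. The check is a comparison of definitions.

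**Step 1: where each attribution level falls.**

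| Recorded attribution | Section 8, 24-hour report rule (fatal or life-threatening) | Section 9.3.1, related table |
|---|---|---|
| Possible | Included | Included |
| Probable | Included | Included |
| Definite | Included | Not listed |
| Not specified | Not mentioned | Included by default |

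**Step 2: does anything bring definite back in?**

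- The default in Section 9.3.1 applies only when the relationship is left unspecified. A rating of definite is a specified relationship, so the default does not apply.
- No section says that probable includes definite.
- No section sets out the attribution scale in another way that would close the gap.

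**Step 3: direction of the error.** Let P be the number of events rated possible or probable, U the number with no attribution, and D the number rated definite.

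- Related events as written: P + U.
- Related events with definite included: P + U + D.
- Shortfall: D, which is zero or positive. The related-event count can be too low, never too high.

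The same holds for patients. The set counted as written is contained in the set counted with definite included. The shortfall is the number of patients whose only related events are rated definite.

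**Step 4: size of the error.** In event counts the relative shortfall is D / (P + U + D). The documents give no expected or observed value for P, U or D, so no number can be put in. Nor does that fraction carry over to patient-level incidence. A patient with one definite event and one possible, probable or unattributed event is still counted overall. For overall incidence the shortfall would therefore usually be smaller than the event share. For a single adverse event term it could be smaller or larger.

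**Step 5: what else uses this definition.**

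- The table of all adverse events does not depend on attribution, so definite events stay in it.
- Serious event reporting under Section 8 does not depend on attribution, and its 24-hour rule names definite.
- The stopping rule in Sections 4.1 and 9.1.1 refers neither to Section 9.3.1 nor to the three levels.

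Only the treatment-related incidence table is exposed.

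**The case against.** The strongest reply is that this is a drafting slip that would do no harm in practice. Section 9.3.1 counts even unattributed events as related, so its intent is plainly inclusive, and a sensible programmer would add definite. The word appears in the documents only in the 24-hour reporting rule of Section 8. Adverse event reporting follows an institutional policy that is not reproduced, so it is not certain that the form used for the analysis offers a definite category. The safety analysis is descriptive, and no test or sample size rests on the definition.

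Much of this stands. It limits the claim to what the text would do if applied literally, and it limits the consequence to one table. It does not remove the defect. The text does not authorise the correction, so an analyst must either follow a rule that is wrong or depart from it without documentation.

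Two stronger readings are tempting and should be resisted.

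- A reader might infer that related-event incidence is understated by some percentage equal to the share of definite ratings. The documents give no such share, and an event share is not a patient-level incidence.
- A reader might infer that the stopping proportions are undercounted too, and that the Section 9.3.1 set should be used there. Those rules count only toxicity judged directly related, of grade 3 or 4 and lasting more than 2 weeks, with no link to the attribution levels. Importing the Section 9.3.1 set, with its possible and unattributed events, could change a clinical rule whose limits are reached at small counts. At 6 patients, 0.30 × 6 = 1.8, so the cohort I limit is met at 2 patients; 0.15 × 6 = 0.9, so the cohort II limit is met at 1.

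**Conclusion.** Wrong as written. Section 9.3.1 omits an attribution level that Section 8 recognises, and no other text restores it. Applied literally, the rule would leave definite events out of the treatment-related incidence table while including unattributed ones. The direction is certain, since the table can only understate. The size cannot be derived from the documents.

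The conclusion rests on two conditions: that investigators can record definite, as the wording of Section 8 implies, and that Section 9.3.1 is programmed as it reads. The documents do not establish that definite events will in fact be lost, only that the stated rule would lose them. Neither overall adverse event incidence, serious event reporting nor the stopping rule is affected.

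**What to change.** In Section 9.3.1, define treatment-related events as those rated possible, probable or definite, and keep the existing default for missing attribution. State the attribution scale once and use it in both Section 8 and Section 9.3.1, so that the table and the reporting rule draw on the same levels. This point calls for no change to the stopping rule in Sections 4.1 and 9.1.1.

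The cost is a short edit to the text. It needs no new patients or procedures. Related-event rates may look slightly less favourable than under the present wording.

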9.3.2 Clinical Laboratory Tests

Laboratory test values outside the normal range will be assessed for drug association based on screening and baseline values and for severity based on the normal ranges for the clinical reference laboratory. The incidence of abnormal laboratory values and shift tables relative to baseline will be tabulated.

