3.1 Inclusion Criteria

- A. Must be at least 18 years of age.
- B. Patients must have relapsed/refractory leukemias for which no standard therapies exist. Patients with poor-risk myelodysplasia (MDS) [i.e. refractory anemia with excess blasts (RAEB-1 or RAEB-2) by WHO classification] and chronic myelomonocytic leukemia (CMML) who failed prior therapy are also candidates for this protocol. Relapsed/refractory leukemias include acute non-lymphocytic leukemia (AML) by WHO classification (i.e. ≥ 20% blasts), acute lymphocytic leukemia (ALL), or chronic myelogenous leukemia (CML) in blast crisis. Patients with CML who are resistant to at least two tyrosine kinase inhibitors and have no standard stem cell transplant option are also eligible.
- C. ECOG performance status of 0-2.
- D. A female of childbearing potential must have a negative serum or urine pregnancy test at screening. Women of child-bearing potential (i.e., women who are premenopausal or not surgically sterile) must use acceptable contraceptive methods (abstinence, intrauterine device [IUD], oral contraceptive or double barrier device), and must have a negative serum or urine pregnancy test within 2 weeks prior to beginning treatment on this trial. Sexually active men must also use acceptable contraceptive methods for the duration of time on study.

- E. Must be able and willing to give written informed consent.
- F. In the absence of rapidly progressing disease, the interval from prior treatment to time of study drug administration should be at least 2 weeks for cytotoxic agents, or at least one week for noncytotoxic agents. Persistent clinically significant toxicities from prior chemotherapy must not be greater than grade 2.
- G. Patients must have the following clinical laboratory values unless considered due to leukemic organ involvement:
 - 1. Serum creatinine ≤ 2.0 mg/dl.
 - 2. Total bilirubin ≤ 1.5x the upper limit of normal unless considered due to Gilbert's syndrome or hemolysis.
 - 3. Alanine aminotransferase (ALT), and aspartate aminotransferase (AST) \leq 2.5x the upper limit of normal unless considered due to organ leukemic involvement (then \leq 5x the upper limit of normal).
 - H. Patients with active CNS disease are included and will be treated concurrently with intrathecal therapy. INCB018424 will not be administered by intrathecal route.

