6.1.4.2 Platelet response (HI-P)

Major response: For patients with a pretreatment platelet count less than 100×10^9 /L, an absolute increase of 30×10^9 /L or more; for platelet transfusion-dependent patients, stabilization of platelet transfusion independence.

Minor response: For patients with a pretreatment platelet count less than $100x10^9/L$ a 50% or more increase in platelet count with a net increase greater than $10 \times 10^9/L$ but less than $30 \times 10^9/L$

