6.1.4.3 Neutrophil response (HI-N)

Major response: For absolute neutrophil count (ANC) less than 1.5×10^9 /L before therapy, at least a 100% increase, or an

absolute increase of more than $0.5 \times 10^9/L$, whichever is greater.

Minor response: For ANC less than 1.5×10^9 /L before therapy, ANC increase of at least 100%, but absolute increase less than 0.5×10^9 /L.

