8.1 Expedited Adverse Event Reporting

Leukemia associated symptoms are not to be reported as adverse events on this protocol. Myelosuppression and associated complication are expected events during leukemia therapy and are part of the treatment success (marrow emptying of leukemia cells). Therefore, myelosuppression and associated complications such as fever, infections, bleeding, and related hospitalization will be reported in the study summary. Only prolonged myelosuppression, as defined by the NCI criteria specific for leukemia, i.e. marrow cellularity <5% on day 42 or later (6 weeks) from start of therapy without evidence of leukemia, will be reported as an SAE and considered in defining the maximum tolerated dose (MTD) and dose-limiting toxicity (DLT). Admission to the hospital for administration of a new cycle of treatment does not require expedited reporting. SAEs occurring in patients registered to the trial but not receiving any protocol agents (ie occurring before protocol treatment) do not require expedited reporting.

For this protocol, the following adverse events are specifically excluded from expedited AE reporting:

			Hospitalization/	
CTCAE Category	Adverse Event	Grade	Prolongation of Hospitalization	Comments
Blood/Bone marrow/ Infection	↓Hemoglobin, leukocytes (total WBC), lymphopenia, ↓neutrophils/ granulocytes (ANC/AGC), ↓ platelets, fever, sepsis	1-4	Yes	Do not require expedited reporting
				Hospitalization for grade
Gastrointestinal	Diarrhea, nausea, vomiting, stomatitis	1-3	Yes	3 AEs does not require expedited reporting Do not require
Metabolic/laboratory	↓K,↓Mg, ↓Na, ↓glucose, ↑K, ↑Mg, ↑glucose, ↑uric acid,↑LDH Or other metoablic indeces	1-4	Yes	expedited reporting unless hospitalized for management

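### Section 9.3.2 rates laboratory severity by normal ranges and leaves its shift tables undefined, so no committed table shows how far blood counts fall in patients who enter already low

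*Combined protocol and SAP*

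**What the plan says.** Section 9.3.2 makes three commitments for laboratory tests. Out-of-range values are assessed for association with the drug by reference to screening and baseline. They are assessed "for severity based on the normal ranges for the clinical reference laboratory". And "The incidence of abnormal laboratory values and shift tables relative to baseline will be tabulated". The section does not mention CTCAE grade, does not define the shift categories, and does not say whether the on-treatment value is the worst, the last or one per visit.

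Elsewhere:

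- Section 9.3 says that safety data, including routine laboratory tests, are summarised with statistics such as means and frequencies.
- Section 9.3.1 grades adverse events by CTCAE v3.0. The table it promises is of incidence: "The incidence of adverse events and treatment-related adverse events will be tabulated".
- Section 8.1 says "Leukemia associated symptoms are not to be reported as adverse events on this protocol", and that "myelosuppression and associated complications such as fever, infections, bleeding, and related hospitalization will be reported in the study summary". Its table lists decreases in hemoglobin, white cells, neutrophils and platelets as adverse events of grade 1-4 and exempts them from expedited reporting only.
- Section 4.5 manages counts by grade. Grade 4 neutropenia or thrombocytopenia lasting beyond 2 weeks allows dose modification, and recovery may be judged by closeness to the starting grade.

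**The concern.** A normal range separates normal from abnormal. It does not define degrees of severity below the lower limit, and that is where many of these patients may start. For a patient who enters with a low count, an incidence-of-abnormality table cannot show how much further the count fell. A shift table built on low, normal and high cannot show it either.

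Safety and tolerability form the first secondary objective (Section 1), and falling counts are a known effect of the drug. Section 2.2.3 reports that in the myelofibrosis study dosing at 50 mg BID was halted after two of four patients had significant falls in neutrophils and platelets. The starting dose here, 25 mg BID, has a better record: three patients were treated for over five months without notable toxicity, and three more for at least 1 month. But Section 4.1 allows escalation to 50 mg BID on progression for patients outside chronic-phase CML. How far counts fall from entry is therefore something that the final report should be able to show.

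**Working it through.** The plan states no figure on this point, so there is none to reproduce. The sample size inputs do not enter.

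**1. Can patients enter with low counts?** Section 3.1.G reads "Patients must have the following clinical laboratory values unless considered due to leukemic organ involvement" and then limits creatinine, bilirubin and transaminases. It lists no ANC, platelet or hemoglobin minimum. The response criteria foresee low counts: Section 6.1.4.2 begins "For patients with a pretreatment platelet count less than" 100 x10^9/L, and Section 6.1.4.3 begins "For absolute neutrophil count (ANC) less than" 1.5 x10^9/L. Section 6.1.4.1 covers hemoglobin below 11 g/dL and transfusion dependence. So the answer is yes. The documents do not give the proportion, so no expected number of patients is offered.

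**2. What would each scale show?** Percent change = (on-treatment - baseline) / baseline. The cut-points below are assumptions, because the documents give none. Platelets: lower limit 150, then 75, 50 and 25 x10^9/L. ANC: lower limit 2.0, then 1.5, 1.0 and 0.5 x10^9/L.

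| Count (x10^9/L) | Percent change | Normal-range shift | Grade shift |
|---|---|---|---|
| Platelets 90 to 80 | (80 - 90)/90 = -11.1% | low to low | 1 to 1 |
| Platelets 90 to 15 | (15 - 90)/90 = -83.3% | low to low | 1 to 4 |
| Platelets 60 to 10 | (10 - 60)/60 = -83.3% | low to low | 2 to 4 |
| ANC 1.2 to 0.3 | (0.3 - 1.2)/1.2 = -75.0% | low to low | 2 to 4 |
| Platelets 20 to 5 | (5 - 20)/20 = -75.0% | low to low | 4 to 4 |
| ANC 0.4 to 0.1 | (0.1 - 0.4)/0.4 = -75.0% | low to low | 4 to 4 |

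On the normal range all six rows look the same. Grade separates the second, third and fourth rows from the first. It does not help in the last two rows, where the patient starts at the top grade, so grade alone is not a complete remedy. The low-to-low result needs only that the baseline is below the lower limit; it does not depend on the assumed grade boundaries.

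**3. Are the data there for a worst value?** The study calendar schedules CBCs on days 8, 15 and 22 of Cycle 1 (3) and on days 1, 8, 15 and 22 of Cycles 2 and 3 (4 x 2 = 8). That is 3 + 8 = 11 on-treatment counts for a patient who completes three cycles, and fewer for one who stops earlier. Table 5.1 requires the pre-treatment CBC to be repeated if it is more than 24 hours old at the first dose, which gives a clean baseline.

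**4. Does another planned output show depth of fall from entry?**

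| Route | What it gives | What it leaves out |
|---|---|---|
| 9.3 | Means and frequencies | Individual nadirs; no laboratory change measure is named, whereas 9.3.3 names mean change from baseline for vital signs |
| 9.3.1 | CTCAE-graded adverse events, incidence tabulated | Tabulation by grade is not stated; entry value is not part of the table |
| 8.1 | Myelosuppression in the study summary | Format and measure are not stated |
| 4.1, 4.2 and 9.1.1 | Action on grade 3 or higher toxicity | These are decision rules and describe no depth of fall |

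Each route carries part of the information. None commits to a table of fall relative to entry.

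**The case against.** The strongest reply is that the harm depends on a table format that the plan does not specify. Section 9.3.2 leaves the shift categories open, so grade-based shift tables on worst values are not ruled out, and these would show most of what is missing. The same section already plans a comparison with screening and baseline values when judging drug association. On this view only table-shell detail is lacking. It stands in part: the point is conditional. But the section does state a severity basis, and that basis is normal ranges, so naming a better one is more than filling in a blank.

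A reader might infer something stronger: that deep count falls go unseen in this trial, or that Section 8.1 removes them from the record. The documents do not support that. The Section 8.1 sentence on leukemia-associated symptoms is about symptoms, and the table there treats count falls as graded adverse events, exempt only from expedited reporting. Section 9.3.1 grades adverse events. Sections 4.1 and 9.1.1 stop a cohort on drug-related grade 3-4 toxicity lasting over 2 weeks (30% or more of patients in cohort I, 15% or more in cohort II, after 6 are enrolled), and Section 4.2 sets boundaries for considering dose reduction. None of these depends on Section 9.3.2.

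It is also fair to say that better tables would not separate drug effect from disease, and that transfusion and growth factors, both permitted by Section 4.3, alter the values. Both limits stand and belong in a table note.

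**Conclusion.** The point holds as a minor safety-reporting improvement. Section 9.3.2 names a severity basis that cannot rank further falls in patients already below the lower limit, and no other planned table fills that place. Sample size, stopping rules and response analysis are unaffected.

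Two conditions apply. Some patients must enter with low counts, which the criteria permit and foresee, though the share is unknown. And the shift categories must follow the stated normal-range basis. If they are instead CTCAE grades on the worst value, the gap shrinks to patients already at the top grade. The finding concerns how depth of fall is displayed; it does not show that marrow toxicity would be missed.

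**What to change.** In Section 9.3.2:

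- Grade ANC, platelets and hemoglobin by CTCAE v3.0, the version that Section 9.3.1 already uses; Section 4.5 also manages dosing by CTC AE grade.
- Define baseline as the last CBC before the first dose, and tabulate baseline grade against worst on-treatment grade by disease arm.
- Because patients at the top grade cannot shift, also summarise nadir and percent change from baseline to nadir for ANC and platelets.
- Keep normal ranges for analytes without CTCAE grades, and state the shift categories used for them.
- Add a note that transfusion and growth factors affect the values and that the tables do not separate drug effect from disease.

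The cost is a few sentences and a few extra descriptive tables from CBCs already scheduled. No new visits, tests or patients are needed. Formal flagging of affected values and paired with-and-without analyses are not required.
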